assigned by randomization ** (triptorelin for 5 years; surgical **C** OFS plus oophorectomy; ovarian Exemestane for 5 years irradiation)

* Patients may have received tamoxifen or anti-aromatase agent prior to randomization

** OFS = ovarian function suppression (triptorelin for 5 years OR surgical oophorectomy OR ovarian irradiation)

Treatment Schedules

- **Radiotherapy:** Radiation therapy to the conserved breast is required. Radiation therapy to the chest wall following mastectomy is optional (if given, it may also include nodal fields). Radiation therapy may be given either after all chemotherapy or integrated into chemotherapy (if regimen is considered safe by the investigator). Radiation therapy may be concurrent with trial hormonal therapy.
- **Chemotherapy:** Patients in the chemotherapy stratum must have completed adjuvant (and/or neoadjuvant) chemotherapy prior to randomization. A planned duration of months if an anthracycline was included (e.g. 4 cycles of EC or AC) of 4 months if no anthracycline was given (e.g. 6 cycles of CMF) is recommended. If an anthracycline was used, an epirubicin-containing regimen is recommended. The final dose of chemotherapy must be less than 8 months prior to randomization.

Adjuvant Endocrine Therapy:

Tamoxifen:	Tamoxifen 20 mg orally daily until 5 years from date of randomization, unless relapse or intolerance should occur earlier.
Exemestane:	Exemestane (Aromasin [®]) 25 mg orally daily, preferably after food, until 5 years from date of randomization, unless relapse or intolerance should occur earlier. Exemestane should begin after initiating ovarian function suppression.
Triptorelin:	Triptorelin (GnRH analogue) 3.75 mg by intramuscular injection every 28 days for 5 years from randomization, unless relapse or intolerance should occur earlier or surgical oophorectomy or ovarian irradiation is subsequently performed. Triptorelin (Decapeptyl Depot [®] intramuscular or Trelstar Depot [®] intramuscular) will be supplied by the study for use as GnRH analogue.
Surgical oophorectomy:	Bilateral surgical oophorectomy via laparotomy or laparoscopy.
Ovarian irradiation:	Bilateral ovarian irradiation. Biochemical verification of ovarian function cessation is required after two months (see Section 5.1.3).

TABLE OF CONTENTS

Sectio	on]	Page	
	1	Introduction	•••••	12	2
Trial	object	tives 16	3	Patier	nt
select	tion				
		3.1 Criteria for patient eligibility		16	
	3.2	Criteria for patient ineligibility	18		

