5.1.5 Exemestane (Aromasin[®]) 25 mg orally daily, preferably after food, until 5 years from date of randomization, unless relapse or intolerance should occur prior to 5 years. It is suggested that exemestane begin approximately 6 to 8 weeks after initiation of ovarian function suppression; however, it may begin immediately after, but no later than 10 weeks after, initiation of ovarian function suppression. [Note that exemestane administered to a premenopausal woman in the absence of ovarian function suppression (i.e., if GnRH analogue is discontinued) is not an effective treatment.] Patients who were receiving tamoxifen therapy at the time of randomization may continue such therapy until exemestane is initiated. Exemestane will be provided free of charge.

5.1.6 Radiotherapy: The role of radiotherapy is not assessed in the present trial but radiotherapy should be used according to accepted guidelines. Radiation therapy to the conserved breast is required.

Radiation therapy to the chest wall following mastectomy is optional and nodal fields may be treated together with the conserved breast or the chest wall.

Radiation therapy may be given either after all chemotherapy or integrated into chemotherapy (if the combination is considered safe by the investigator).

Radiation therapy may be concurrent with trial hormonal therapy or given before starting tamoxifen or exemestane, according to institutional practice. A patient may be randomized prior to completing radiation therapy in order to meet the time frame for randomization (section 3.1.1) and then initiate oral trial hormonal therapy when radiation therapy is completed if this is institutional practice. However, patients randomized to ovarian function suppression and planning to receive triptorelin (GnRH analogue) injections should commence those as soon as randomized.

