8.1 Case report forms schedule—SOFT

The Data Management Manual for this trial contains instructions for submitting forms using the DataFax system.

RANDOMIZAT	TON FORMS	
Form IC	Informed Consent Form	Obtain before randomization and keep with patient records.
Forms 24QLC, 24-QLM, 24- QLS	QL Core and QL Module Forms; QL Supplement Form (for English-speaking Centers only).	DataFax baseline QL forms (see exceptions in Section 3.1.7). These forms are also required during follow-up (see instructions below).
Form 24-A	Confirmation of Registration Form	Fill in before contacting your Randomization Center or entering the IBCSG Registration/Randomization system to randomize. DataFax completed form for all patients randomized.
BASELINE FO	RMS	
Form 24-B	Clinical Form	DataFax within 1 month of randomization.
Form 24-C*	Surgery Form	DataFax within 1 month of randomization.
Form 24-H	Prior Treatment History Form	DataFax within 1 month of randomization.
Form 24-F*	Hormone Receptor Form	DataFax within 1 month of randomization with the hormone receptor report.
Form 24-P*	Pathology Form	DataFax within 1 month of randomization with a copy of the original pathology report.
Form 24-AE	Adverse Event Form	Complete prior to starting protocol treatment (tamoxifen, exemestane, OFS) and DataFax within 1 month of randomization. This form is also required at follow-up (see instructions below.)
Form 24-CCM	Concomitant Medications Form	Complete prior to starting protocol treatment (tamoxifen, exemestane, OFS) and DataFax within 1 month of randomization. This form is also required at follow-up (see instructions below.)
FOLLOW-UP F	FORMS	
Form 24-E	Follow-Up Form	DataFax every 3 months in Year 1, every 6 months during Years 2- 6, and yearly thereafter.
Form 24-OFS	Ovarian Function Suppression Form	DataFax at each follow-up period until completion of OFS.
Form 24-TE	Tamoxifen/Exemestane Form	DataFax at each follow-up period until the completion of tamoxifen and/or exemestane.
Form 24-AE	Adverse Event Form	DataFax at each follow-up period during protocol therapy (tamoxifen, exemestane, OFS), and with Form 24-E at 6 and 12 months after the last dose of protocol therapy. This form is also required at baseline.
Form 24-CCM	Concomitant Medications Form	DataFax at each follow-up period during protocol therapy (tamoxifen, exemestane, OFS), and with Form 24-E at 6 and 12 months after the last dose of protocol therapy. This form is also required at baseline.

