### TEXT Schema:

\* Randomization prior to receiving any adjuvant systemic therapy

\*\*CT (chemotherapy) is determined by investigator/patient choice and if used, should begin at the same time as triptorelin.

[figure not shown]
\*\*\*Tamoxifen or exemestane should start after adjuvant chemotherapy has been completed or approximately six to eight weeks after the initiation of triptorelin, whichever is later.

IBCSG 25-02 (TEXT) is an international, non-blinded, randomized phase III trial designed to investigate the efficacy the aromatase inhibitor (AI) exemestane with OFS, achieved by long-term use of GnRH analogue, compared with tamoxifen+OFS. TEXT focuses the AI question on premenopausal patients whom the physician feels OFS is most appropriate from the start of adjuvant therapy. Eligibility required enrollment within 12 weeks of definitive surgery and excluded patients who had already received any (neo)adjuvant chemotherapy or endocrine therapy. Randomization used 1:1 allocation and stratified by whether adjuvant chemotherapy was planned (no; yes), and number of positive nodes (0; 1 or more). Patients would either receive no chemotherapy or commence chemotherapy at the same time as GnRH analogue is initiated. Patients had to use GnRH analogue for at least 6 months and then could change to permanent OFS with surgery or radiation at any time thereafter.

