### SOFT Schema:

\* Patients may have received tamoxifen or an anti-aromatase agent prior to randomization

\*\* OFS = ovarian function suppression (triptorelin for 5 years OR surgical oophorectomy OR ovarian irradiation)

IBCSG 24-02 (SOFT) is an international, three-arm, non-blinded, randomized phase III trial designed to investigate the role of OFS and the role of the AI exemestane, originally planned with three primary comparisons: tamoxifen+OFS versus tamoxifen alone; exemestane+OFS versus tamoxifen alone; and exemestane+OFS versus tamoxifen+OFS. SOFT focuses the OFS question on those who biologically would be most likely to benefit, i.e., women with endocrine-responsive breast cancer with premenopausal status either after completion of (neo)adjuvant chemotherapy or following surgery alone.

Eligibility required enrollment either: (a) within 8 months of the final dose of chemotherapy once premenopausal status was confirmed by estradiol levels (e.g., patients with temporary chemotherapy-induced amenorrhea who regained premenopausal status within 8 months were eligible); or (b) within 12 weeks of definitive surgery if no adjuvant chemotherapy was to be given. Patients could have received adjuvant oral endocrine therapy (but not GnRH analogues) for up to 8 months prior to randomization. The 8-month criterion was an early protocol amendment (from 6 months) to overcome logistical challenges of enrolling a patient who presented after regaining premenopausal status at a 6-months post-chemotherapy standard-of-care visit.

Randomization used 1:1:1 allocation, and was stratified according to prior (neo)adjuvant chemotherapy (yes;no), lymph node status (0; 1+) and intended method of OFS (GnRH analogue, oophorectomy; ovarian irradiation). For patients randomized to receive OFS, the use of GnRH analogue, bilateral oophorectomy or bilateral ovarian irradiation was by patient preference and patients who began with GnRH analogue could opt to undergo surgery or irradiation at any time.

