### 2.6.5.2 AE analysis

Targeted AEs, and other grade 3-5 AEs, are collected on CRFs, until 1 year after the cessation of all protocol treatment. The grade and causality attribution are recorded according to the NCI Common Terminology Criteria for Adverse Events (CTCAE) version 3.0. In TEXT, chemotherapy-related AEs are collected separately.

The targeted AEs will be summarized by AE type and maximum grade over time, regardless of causality attribution. The maximum grade consolidates the reports of a given type of AE for a patient over time since randomization (i.e., baseline reports are excluded) by taking the maximum across time (i.e., a patient appears only once for a given type of AE). Patients with reports of multiple AEs of different types are reported multiple times under the relevant AE categories. Maximum grade 0 indicates that the AE type has not been reported.

Note, during a period of trial conduct, the IBCSG audit team was asking sites to record grade 3+ weight gain and obesity as other AEs; discussed among StatC/DMC/CC that CRFs record weight serially on E-form and any analysis of weight changes and/or obesity [in these or other IBCSG adjuvant trials] would use the actual weight, not the AE; as a result the audit team changed their practice. Therefore the weight change and obesity “other grade 3+” AEs will be deleted from dataset before summarizing other grade 3+ AEs because the incidence will not be interpretable.

Tables:

- AI Question (E+OFS vs T+OFS)
  - Targeted AEs reported according to treatment group (N; %)
  - Targeted AEs reported according to trial & treatment group (N;%)
  - Targeted AEs reported according to cohort & treatment group (N;%)

- Tables above repeated for the subset of events deemed possibly, probably or definitely related to study treatment(s)
- SOFT (E+OFS vs T+OFS vs T)
  - Targeted AEs reported according to treatment group (N; %)
  - Targeted AEs reported according to chemo strata & treatment group (N;%)
  - Tables above repeated for the subset of events deemed possibly, probably or definitely related to study treatment(s)

Other grade 3 or higher AEs are also requested on CRFs, by write-in text. All will be tabulated, similarly according to max grade, but the intention is to focus on those deemed possibly, probably or definitely related to study treatment(s), which will also be tabulated.

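### The targeted-AE tables make no use of the baseline AE form, so any-grade rates mix symptoms already present at entry with new or worsened ones

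*SAP*

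**What the plan says.** SAP 2.6.5.2 takes one value per patient and AE type, consolidated "over time since randomization (i.e., baseline reports are excluded) by taking the maximum across time". The main tables are "summarized by AE type and maximum grade over time, regardless of causality attribution". They are repeated for events judged at least possibly related to treatment. They are also split by trial and by cohort for the AI Question, and by chemotherapy stratum for SOFT.

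A baseline grade exists for comparison. Protocol 7.1 makes the AE form mandatory at month 0, and Protocol 8.1 says of Form 24-AE: "Complete prior to starting protocol treatment (tamoxifen, exemestane, OFS) and DataFax within 1 month of randomization". The supplied SAP plans neither a baseline AE table nor a change-from-baseline table.

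Entry conditions differ between the trials. For SOFT the SAP states: "Patients could have received adjuvant oral endocrine therapy (but not GnRH analogues) for up to 8 months prior to randomization". The protocol schema adds: "Patients may have received tamoxifen or anti-aromatase agent prior to randomization". SOFT also takes patients after chemotherapy. Protocol 5.1.5 allows some earlier treatment to run on: "Patients who were receiving tamoxifen therapy at the time of randomization may continue such therapy until exemestane is initiated". TEXT, according to SAP 1.2, excluded anyone with earlier adjuvant or neoadjuvant chemotherapy or endocrine therapy.

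Protocol 7.2 treats an AE as something that arises from the first dose of study medication onward.

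**The concern.** A woman who enters SOFT with grade 2 hot flushes and still has grade 2 hot flushes a year later is tabulated as a grade 2 AE of her assigned arm. Under Protocol 7.2 an unchanged symptom that predates the first dose is not an AE of the trial treatment. The types reported most often in the first analyses (SAP 1.3.1 and 1.3.2) were hot flushes, musculoskeletal symptoms and hypertension, all of which can exist before entry and persist.

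What is at stake is how the any-grade percentages are read. Readers will take them as the side-effect burden each regimen produces, and may set SOFT rates beside TEXT rates. The update report leaves out post-treatment AEs (SAP 2.6.5.3) and gynecologic and fertility data (SAP 2.6.7), so the tables in 2.6.5.2 carry most of its AE evidence.

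**Working it through.** **The plan's own figure.** SAP 1.3.2 gives grade 3-5 targeted AEs in 31% (T+OFS) and 24% (T): a difference of 7 points and a ratio of 31/24 = 1.29. These cannot be rebuilt, because no AE counts or denominators are given.

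**Model.** Let b be the share of patients who already have the AE at entry and keep it at the same grade, equal in both arms by randomization. Let r1 and r0 be the new-onset rates among patients free of it at entry.

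- Current table: b + (1 - b)r
- Worsened-from-baseline, all patients: (1 - b)r
- Risk difference in both: (1 - b)(r1 - r0)
- Ratio in the worsened table: r1/r0

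The current table exceeds the treatment-emergent rate by exactly b in each arm. The two tables share the same risk difference; only the absolute rates and the ratio differ.

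**Any-grade illustration.** The documents give no value of b and no new-onset rates. Assume r1 = 45%, r0 = 30% and b from 0 to 50%.

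| b | Current table | Ratio | Worsened, all patients | Ratio | Difference, either table |
|---|---|---|---|---|---|
| 0 | 45% vs 30% | 1.50 | 45% vs 30% | 1.50 | 15 points |
| 20% | 56% vs 44% | 1.27 | 36% vs 24% | 1.50 | 12 points |
| 40% | 67% vs 58% | 1.16 | 27% vs 18% | 1.50 | 9 points |
| 50% | 72.5% vs 65% | 1.12 | 22.5% vs 15% | 1.50 | 7.5 points |

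If only half of the baseline symptoms persist, and the rest resolve and then carry the same new-onset risk, b is halved: 40% prevalence gives the 20% row.

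**SOFT beside TEXT.** Suppose the same drug effect, r = 45%, with b = 20% in SOFT and 0 in TEXT (both assumed). The current table shows 0.20 + 0.80 x 0.45 = 56% against 45%. The all-patient worsened table shows 36% against 45%. Only the rate among patients free of the AE at entry agrees, at 45% in both.

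**Grade 3-5.** Apply the model to 31% and 24%, with b now the share already at grade 3 or higher at entry and staying there. Among patients free of it at entry, r = (p - b)/(1 - b), where p is the reported rate:

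- b = 2%: 29.6% vs 22.4%, difference 7.1 points, ratio 1.32
- b = 5%: 27.4% vs 20.0%, difference 7.4 points, ratio 1.37
- b = 10%: 23.3% vs 15.6%, difference 7.8 points, ratio 1.50

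Over all patients the worsened-from-baseline difference stays at 7 points throughout; at b = 10% it is 21% against 14%.

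**When the model fails.** Suppose 40% enter with lower-grade symptoms and reach grade 3 or higher in 45% vs 30%, while the others do so in 21.7% vs 20%. Overall that gives 0.4 x 45 + 0.6 x 21.7 = 31% against 0.4 x 30 + 0.6 x 20 = 24%. The difference is 7.0 points overall but 1.7 among those free of symptoms at entry. Here patients with baseline symptoms enlarge the contrast.

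**The case against.** A reader might infer that the planned tables bias the treatment contrasts and hide the tolerability cost of adding OFS. The documents do not support that. Randomization balances entry symptoms in expectation, and the all-patient risk difference is the same with or without the baseline cases. The larger 15-point figure describes only patients free of the symptom at entry. Dilution of the ratio is conditional on persistence at the same grade and equal effects in both kinds of patient; the last calculation shows the opposite can occur.

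Other objections have force:

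- The main tables are expressly all-causality, so carried-over symptoms are counted as reports, not declared drug effects. Related-only tables are planned too. Attribution in a non-blinded trial is, however, a weak substitute for a recorded baseline grade.
- Splits by trial, cohort and chemotherapy stratum are planned. They expose part of the mixing, but none separates prior endocrine therapy or removes baseline cases.
- Prior therapy in SOFT was permitted, not universal, and SOFT has a no-chemotherapy cohort. Tamoxifen continued before exemestane is limited to 10 weeks after OFS starts (Protocol 5.1.5), within a five-year regimen.
- For a patient already on tamoxifen and assigned tamoxifen, persisting symptoms may be true effects of the assigned drug. Subtracting baseline removes them in SOFT but not in TEXT. This argues against replacing the main table, as does continuity with the first report.
- The SAP for the first report, to which this one defers for some details, was not supplied and may contain a baseline AE summary.

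**Conclusion.** The point stands as one of interpretation. Any-grade targeted-AE rates under SAP 2.6.5.2 combine symptoms already present with new or worsened ones, overstate treatment-emergent incidence by the persisting baseline share, and are not directly comparable between SOFT and TEXT. Risk ratios move toward 1 if carry-over persists equally across arms.

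The actual size is unknown because baseline prevalence is not given; every figure above rests on assumed prevalence, persistence and new-onset rates. For grade 3-5, an assumed carry-over of 2-10% moves the stated 7.0 points only to 7.1-7.8 among patients free of such an AE at entry, though the ratio moves from 1.29 to 1.32-1.50. For AE types that are rarely present at entry, the effect is negligible.

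A reader might also tie this to the protocol's objective on late side effects of early menopause. That link is not shown: Protocol 7.1 places AEs after completed treatment on Form E, and SAP 2.6.5.3 leaves them out of the update. No efficacy conclusion is touched.

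**What to change.** Keep the current maximum-grade tables as the main display, for continuity with the first report. Add to SAP 2.6.5.2:

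- (a) the baseline grade distribution of each targeted AE by arm, trial and cohort. This also checks balance: the baseline form precedes treatment, but not necessarily knowledge of the allocation.
- (b) a companion table that counts an AE type only when its maximum post-baseline grade exceeds the baseline grade, for all patients and again among those free of that AE at baseline. The second version is needed for reading SOFT beside TEXT.
- (c) a stated rule for missing baseline forms. One workable rule is to treat the baseline grade as 0 in the all-patient version, leave these patients out of the free-at-entry version, and report their number by arm.
- (d) a note that the companion table omits persisting symptoms that may be true drug effects in patients already on tamoxifen and assigned tamoxifen, so the two tables must be read together.

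The cost is SAP wording, one merge with a form already collected, and some additional tables. No new data are needed.

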5.2 Side effects of study drugs

5.2.1 GnRH analogue: The most common side effects are hot flushes, sweating, amenorrhea, fertility impairment, decreased libido and vaginal dryness and/or dyspareunia. Less frequent side effects are headache, tiredness, mood changes, sleep disturbance, nausea, back or joint pain, local injection site reaction, weight gain and slight rise in cholesterol. Loss of bone mineral density can occur.

In clinical trials in advanced disease adverse events (AEs) were generally mild to moderate and rarely severe enough to require discontinuation of treatment. Adverse experiences that have been seldom reported include: skin rash, allergic and anaphylactic reactions including angioedema, hypo- or hypertension, and elevated liver enzymes.

GnRH analogue is contraindicated in pregnancy and lactation. Cases of pregnancy have occurred in women receiving regular injections of GnRH analogue [22]. The role of nonhormonal contraception should therefore be discussed.

Following a safety review of several published studies in men with prostate cancer receiving GnRH agonists, on 20 October 2010, the US FDA required manufacturers of GnRH agonists to add new safety information about increased risk of diabetes and certain cardiovascular diseases in men receiving GnRH agonist for the treatment of prostate cancer to the Warnings and Precautions section of the drug labels. The FDA"s 3 May 2010 Drug Safety Communication, last updated 4 January 2011, about the Ongoing Safety Review of GnRH Agonists noted, "There are no known comparable epidemiologic studies evaluating the risk of diabetes and cardiovascular disease in agonists." (http://www.fda.gov/Drugs/DrugSafety/ women taking GnRH PostmarketDrugSafetyInformationforPatientsandProviders/ucm209842.htm; accessed 21 February 2011) Therefore, no changes are recommended concerning the management of patients on this study. Nevertheless, in addition to the cardiovascular and other targeted adverse events already collected, we will prospectively capture adverse event information specifically on hyperglycemia and glucose intolerance (diabetes) and the use of anti-diabetic drugs as concomitant medications.

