- B. Estradiol must be in the premenopausal range within 12 weeks of surgery or for patients who have received chemotherapy between 2 weeks and 8 months after the final dose of chemotherapy (Section 3.1.1). It is recommended to determine E₂ level as close to randomization as possible. The only patients who do not require testing of estradiol (E₂) to confirm premenopausal status are those who did NOT receive chemotherapy and who have been menstruating regularly during the 6 months prior to randomization and have not used any form of hormonal contraception or any other hormonal treatments during the 6 months prior to randomization.
- C. Adverse events should be graded using the NCI CTCAE version 3.0 (Appendix II). The following list gives targeted adverse events that should be recorded on the CRF at any time: Vaginal dryness and/or treatment to alleviate Decreased libido (sexual interest) Urinary incontinence Vasomotor menopausal symptoms (hot flashes/flushes, night sweats) and/or treatment to alleviate Osteoporosis and/or treatment to prevent/alleviate Bone fracture Dyspareunia (pain or discomfort with intercourse) and/or treatment to alleviate Musculoskeletal symptoms (myalgia, arthralgia (joint pain), stiffness not including bone fractures) and/or treatment to alleviate Depression CNS cerebrovascular ischemia CNS hemorrhage Hypertension Cardiac ischemia/infarction Thrombosis and/or embolism Nausea Insomnia Sweating Fatigue Allergic reaction and/or hypersensitivity Injection site reaction Glucose Intolerance (Diabetes) and/or anti-diabetes treatment Hyperglycemia Other Grade 3 or higher adverse events
- D. Late adverse events (adverse events occurring after trial treatment is completed) should be recorded on Follow-up Form E.
- E. Hematology must be done within 2 months prior to randomization and whenever medically indicated.

F. Blood chemistry (includes liver function tests with alkaline phosphatase) must be done within 2 months prior to randomization and whenever medically indicated.

Radiological assessments

- G. A bilateral mammography must be taken within one year prior to randomization. A mammography of the conserved and contralateral breast is recommended at yearly intervals or should be done according to national standards or hospital specific requirements.

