Two-sided alpha level	.0167	.0167	.0167
Power	.80	.80	.80
Required number of events for two arms*	861	522	343
Accrual rate for two arms (pts/year)	400	400	400
Total accrual time (yrs)	5.5	5	4 .5
Sample size (two arms)	2200	2000	1800
Total study duration with 4 interim + 1 final analyses (yrs)*	9.8	6.9	5.4
Total sample size (all 3 arms)	3300	3000	2700

* Under the alternative hypothesis with 4 interim analyses and 1 final analysis [41].

For planning purposes, we will target a 25% reduction in hazard for each of the three comparisons. This will require recruitment for the three arms of **3000 patients** (600 patients per year for 5 years with 1.9 years of additional follow up). Accrual of premenopausal patients with ER-positive tumors to IBCSG Trials VI (N+) and VIII (N-) averaged 222 per year. Applying the 15.6% rate of maintaining menses following chemotherapy to this cohort, we anticipate approximately 35 patients per year from IBCSG institutions. Global participation including the Breast International Group (BIG) and the US Intergroup is required to successfully complete this trial.

The same operating characteristics apply to the second comparison (OFS plus exemestane versus tamoxifen alone) and to the third comparison (OFS + exemestane versus OFS + tamoxifen), when testing for an improvement in 5-year DFS from the baseline value of 67%. If one assumes a 25% reduction in hazard due to the addition of OFS to tamoxifen (and thus an estimated 74.1% 5-year DFS for the OFS + tamoxifen arm), then a further 25% reduction in the hazard for OFS + exemestane compared with OFS + tamoxifen (to 79.8% 5-year DFS) would be detected with 68% power, if the final analysis is performed at 6.9 years from the activation of the study.

The originally planned sample size was 3000. It was projected that 5 years of accrual, plus 1.9 years of additional follow up would be sufficient to observe the 783 target number of DFS events (522 needed for each pairwise comparison). This number of events would provide 80% power to detect a hazard ratio of 0.75 for GnRH + tamoxifen versus tamoxifen alone (74.1% versus 67.0%)

5-yr DFS, respectively) using a 2-sided, 0.0167 level test (adjusting for multiple tests). The study opened to enrollment in August 2003. In January 2011, enrollment was closed with 3066 patients randomized. Due to agreements with pharmaceutical partners and financial constraints, it is not possible to increase patient enrollment.

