## 2.6.5 Adverse Events / Safety

### 2.6.5.1 AE population

The AE population is the subset of patients in the ITT analysis population who started protocol treatment (and have at least 1 post-baseline AE form submitted). **This population will be updated from the first analysis using updated information, as necessary, and any such changes will be included in the report.**

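### Diabetes and hyperglycemia became targeted AEs in SOFT only after accrual closed, so the SAP's percentages for these two items are not incidences since randomization

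*SAP*

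**What the plan says.** - **Addition of the items.** Protocol 5.2.1 reacts to a regulator's safety communication on GnRH agonists, citing a web page "accessed 21 February 2011". It says that "we will prospectively capture adverse event information specifically on hyperglycemia and glucose intolerance (diabetes"), and that this comes "in addition to the cardiovascular and other targeted adverse events already collected". Protocol 7.1, legend C, now lists "Glucose Intolerance (Diabetes) and/or anti-diabetes treatment Hyperglycemia Other Grade 3 or higher adverse events". The protocol is V3.0, Amendment 2, of 14Jul11; SAP 2.1 dates that amendment 24Aug11.
- **Accrual.** Protocol 9.3: "In January 2011, enrollment was closed with 3066 patients randomized". SAP 1.2 gives 17Dec03 and 27Jan11 as the first and last randomization dates.
- **AE forms.** Under Protocol 8.1 the baseline AE form is completed before treatment and sent within a month of randomization. AE forms continue during therapy and at 6 and 12 months after the last dose.
- **Denominator.** SAP 2.6.5.1: "The AE population is the subset of patients in the ITT analysis population who started protocol treatment", with at least one post-baseline AE form. No condition is set on what that form asked.
- **Tabulation.** SAP 2.6.5.2 takes the maximum grade since randomization, excludes baseline reports, and says "Maximum grade 0 indicates that the AE type has not been reported". Write-in events of grade 3 or higher are tabulated separately. Weight gain and obesity write-ins are deleted because they were solicited for only part of the trial and their incidence could not be interpreted. The glycemic items get no such exception.

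**The concern.** One rule is applied to items with different collection histories. For most targeted AEs, no report since randomization is a fair stand-in for no event. For these two it can also mean that the question was not yet on the form. The exclusion of baseline reports, which keeps prior conditions out of the table, has nothing to work on where baseline was never asked.

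Protocol 5.2.1 quotes the regulator as knowing of no comparable epidemiologic studies in women. SOFT has a tamoxifen-alone arm, so its table will be a natural place to look for an effect of ovarian suppression on glucose. A reader would take the percentages as cumulative incidence over about six years, which they are not.

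**Working it through.** The documents state no expected incidence or power for these AEs, so there is no planned figure to reproduce. The check uses dates.

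**1. Order of events.** The page cited in the new text was accessed 25 days after the last randomization (27Jan11 to 21Feb11). The amendment followed 168 days (14Jul11) or 209 days (24Aug11) after the last randomization. So no SOFT baseline form carried the items, and neither did any month-3 form completed on schedule, the last of which fell due about 27Apr11.

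**2. Share of AE time before the items.** Inputs:
- Accrual span T = 7.11 years (17Dec03 to 27Jan11).
- First patient to amendment A = 7.57 years (14Jul11) or 7.69 years (24Aug11).
- AE window 6 years: 5 years of treatment plus the 1 year in SAP 2.6.5.2, assuming full treatment.
- Median follow-up 5.6 years at 31Mar14 (SAP 1.3.3). The first patient had 10.29 years by then, so the median entry time is m = 10.29 − 5.6 = 4.69 years, about August 2008.

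For a patient entering at time t, the uncovered share is min(A − t, 6)/6. She has no window left if t ≤ A − 6. The accrual curve is not given, so two shapes with median m were used.

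*Power curve* F(t) = (t/T)^k, with k = ln 0.5 / ln(4.686/7.113) = 1.661:
- No window left: (1.573/7.113)^1.661 = 8.2%; with the later date, 9.1%.
- Mean entry = 7.113 × 1.661/2.661 = 4.440. Mean time before the items, capped at 6 years = 7.573 − 4.440 − 0.048 = 3.085 years, and 3.085/6 = 51%; with the later date, 53%.

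*Piecewise-uniform*, half of accrual before m and half after:
- No window left: 0.5 × 1.573/4.686 = 16.8%; with the later date, 18.0%.
- Mean entry = 4.121. Capped mean = 7.573 − 4.121 − 0.132 = 3.320 years, and 3.320/6 = 55%; with the later date, 57%.

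(The small subtracted terms are the excess over 6 years among the earliest entrants.) The range is thus 51-57% of AE time and 8-18% of patients. Uniform accrual gives 64-65% and 22-24%, but it implies a median follow-up of 6.7 years, not 5.6. A linear ramp with the later date gives 49% and 6%, but implies about 5.3 years.

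**3. Direction.** As an illustration, assume new onset at 0.5% per year, the power curve and 14Jul11. True 6-year incidence is 1 − exp(−0.03) = 3.0%.

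| Type of event | Recorded |
|---|---|
| Transient, caught only if it occurs after the items began | 1.4% |
| Persistent diabetes, no pre-existing cases | 2.7% |
| Persistent, 1% pre-existing | 3.6% |
| Persistent, 2% pre-existing | 4.5% |

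Transient events are understated. For persistent diabetes the error changes sign at a small baseline prevalence.

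**The case against.** Several points on the other side stand.

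- **Net understatement.** A reader might infer that the table simply understates these AEs. Step 3 shows that this does not follow for diabetes, because uncaptured baseline disease pushes the figure up.
- **Bias between arms.** A reader might also infer a distorted T+OFS versus T comparison. The arms were randomized concurrently 1:1:1, so a calendar gap should fall on them alike. Differential bias needs stopping times that differ by arm, which nothing supplied shows for the updated data. The tables are descriptive and no AE test is planned. What remains is distorted absolute percentages and less sensitivity to a true difference.
- **Severe events.** Grade 3+ events could be written in before the amendment, taking that item as in force throughout (the SAP gives it no start date). They are split across two tables rather than lost.
- **Purpose.** Capture was added as a precaution, and no glycemic outcome is an objective or endpoint.
- **The weight and obesity precedent is partial.** Those were write-ins prompted by auditors, and serial weights were available instead.
- **Unseen sources.** The CRFs and the SAP for the first analysis are not supplied. Retrospective entry cannot be ruled out, although the word prospectively argues against it. The TEXT protocol is not supplied either, so a similar or larger gap in TEXT is a conjecture.

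None of this makes grade 0 a correct label for a patient who was never asked.

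**Conclusion.** The point holds for SOFT as a defect of labelling and denominator. For glucose intolerance (diabetes) and hyperglycemia, the planned percentages are not incidences since randomization. About half or slightly more of AE-collection time (51-57%) precedes the items, and roughly 8-18% of patients have no window after the amendment. Those figures rest on a 6-year window, full treatment, accrual matched to the 5.6-year median, and collection starting at the amendment date. Early stopping would raise the second figure: if 20% stop evenly over years 0-5, 18% becomes 24%. The order of events, and the absence of the items from every baseline form, need only the dates and the prospective wording.

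The direction for diabetes is undetermined, and a between-arm bias is possible but not established. The pooled AI Question tables are affected at least through their SOFT patients. The change should be made, but the efficacy analyses are untouched.

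**What to change.** In SAP 2.6.5.2, for these two items:

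1. Show patients with no AE form dated after collection began as not assessed rather than grade 0. Give the number assessed and the months observed per arm, alongside the full-population figure.
2. Combine earlier grade 3+ write-in reports of the same terms with the targeted reports in one grade 3+ row.
3. Footnote the collection start date and that baseline status is unknown. Flag an item already present on a patient's first such form as onset unknown. Do not call it prevalent or remove it: by the amendment the median patient was about 3 years past randomization, so relabelling would discard genuine on-treatment cases.
4. Do not describe these percentages as incidence since randomization.

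If the items were in fact collected retrospectively, a sentence saying so, with the period covered, would answer most of this. For TEXT, state its own start date.

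The cost is SAP wording and one derivation from form dates, with no new data. The assessed-only figure has a smaller denominator and wider intervals. It also rests on a post-randomization subset that may differ by arm through early discontinuation, which is why the full-population figure stays beside it.
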